4.4. Safety

Data from all subjects who enter the run-in period will be included in the evaluation of safety. Results from the run-in period will be presented separately from the results after randomization. Adverse events will also be reported separately for the two periods.

Treatment emergent adverse effects are defined as adverse events that start after initiation of study drug or adverse events ongoing from screening which worsen in intensity. The definitions of adverse events and serious adverse events are given in the protocol (Sections 4.9, 4.10, and 4.17).

The proportion of subjects experiencing adverse events will be tabulated by treatment received. In the case of adverse events leading to withdrawal or dose changes, the incidence will also be tabulated and reported by treatment group for all events observed during the randomized treatment phase. Summaries of all treatment emergent adverse events, treatment emergent adverse events leading to death, and treatment emergent serious adverse events will also be presented by treatment group.

Laboratory measures and changes from baseline will be summarized by mean, median, SD, minimum, maximum, and number of subject at each visit at which measurements are taken. Pre-specified alterations in laboratory values will be highlighted and summarized by treatment group, including:

1. Increase in transaminase levels (ALT or AST)
 - a. >1.5 to <2 times the upper limit of normal
 - b. more than 2 times the upper limit of normal
2. Platelets
 - a. < 75,000 to 50,000/mm³
 - b. < 50,000/mm³

3. WBC
 - a. $< 4,000$ to $3,000/\text{mm}^3$
 - b. $< 3,000/\text{mm}^3$
4. Reduction in creatinine clearance to
 - a. 30 to $< 40 \text{ ml/min}/1.75\text{m}^2$
 - b. $< 30 \text{ ml/min}$
5. Hematocrit
 - a. $< 27\%$
6. Albumin
 - a. < 0.8 times the lower limit of normal

Vital signs and weight will be summarized at each visit. Physical exam abnormalities at baseline and new or aggravated physical exam abnormalities will be listed, including fevers, cough, shortness of breath, nausea, vomiting, and painful and open mouth sores.

Safety results will be summarized both by randomized treatment assignment and by actual treatment at time of occurrence of an adverse event or measurement of a laboratory value. For the latter, treatment groups are LDM, placebo, and Off Randomized Treatment. Off Randomized Treatment is defined as subjects who have withdrawn from randomized treatment but continue to be followed.

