2.0. ANALYSIS SETS

2.1. Definition of Analysis Sets

The efficacy analyses will be based on an Intention to Treat (ITT) population, defined as all randomized subjects with any follow-up data, analyzed according to their randomized treatment group. Safety analyses will be based upon the Safety population, defined as all subjects entering the study, analyzed according to treatment actually received. Safety analyses will be presented separately for the run-in period and the period after randomization.

Compliance analyses will be based on the Compliance population, defined as all randomized subjects with compliance measures, analyzed according to compliance levels. The primary measure of compliance will be based on pill counts, with participants characterized according to the percent of study pills taken (with denominator that accounts for the directed dose changes) in the interval since the last compliance assessment.

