4.0. ANALYSIS METHODS

4.1. General Principles

In the analysis of efficacy, subjects will be grouped by the treatment to which they were randomized. In the analyses of safety, subjects will be grouped by the treatment received.

All analyses will be stratified by time since the confirmed index myocardial infarction (≤ 6 months vs > 6 months) as well as presence of diabetes or metabolic syndrome at entry.

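### The safety display by treatment at time of event pools all off-treatment events across arms in one column, and the SAP does not say whether this or the by-assignment summary leads

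*Combined protocol and SAP*

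**What the plan says.** The SAP describes the grouping for safety in four places.

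- SAP 2.1 defines the population: "Safety analyses will be based upon the Safety population, defined as all subjects entering the study, analyzed according to treatment actually received".
- SAP 4.1 repeats the rule as a general principle: "In the analyses of safety, subjects will be grouped by the treatment received".
- SAP 4.4 gives the measure for adverse events: "The proportion of subjects experiencing adverse events will be tabulated by treatment received". Its definition of treatment emergence has a start but no end: "Treatment emergent adverse effects are defined as adverse events that start after initiation of study drug".
- The closing paragraph of SAP 4.4 widens this to two displays: "Safety results will be summarized both by randomized treatment assignment and by actual treatment at time of occurrence of an adverse event". On the second display it says: "treatment groups are LDM, placebo, and Off Randomized Treatment". The third column is defined as follows: "Off Randomized Treatment is defined as subjects who have withdrawn from randomized treatment but continue to be followed".

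The definition of the third column does not refer to the arm of origin or to time since the last dose. No section says which of the two displays is the main comparison between arms.

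**The concern.** Leaving study drug is unlikely to be independent of safety in this trial. Protocol 4.7 makes resupply at the four-monthly visits depend on there being no endpoint or laboratory abnormality. Protocol 4.14 issues new packs only if there has been no endpoint or major side effect. Repeated holds can lead to permanent discontinuation. The off-treatment group is therefore a selected one, and the selection may differ between arms.

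Pooling the arms in that group has two consequences for the display by treatment at time of event. The pooled column cannot be compared with anything, because it contains neither arm alone. An LDM event that begins after the stop is also removed from the LDM column, with nothing in the display to trace it back. If this display were read as the main safety comparison, which SAP 2.1 and 4.1 taken alone would allow, the LDM-to-placebo contrast could be distorted.

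**Working it through.** **1. Is there a plan figure to reproduce?** The SAP gives no number for the safety tables. The one related input is the assumption in SAP 1.3 that 10% of the LDM arm will discontinue, beyond those who drop out. The plan uses it once, for the diluted event rate: 3.5 × (1 − 0.30 × 0.90) = 2.555 per 100 person-years, a 27% reduction. This agrees with the stated figure.

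**2. Size of the pooled column.**
- LDM: 0.10 × 3,500 = 350.
- Placebo: the documents give no discontinuation rate. Assuming 5% to 10%, it is 175 to 350.
- Pooled: 525 to 700, of which LDM makes up 350/525 = 67% down to 350/700 = 50%.

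The mix of arms therefore depends on a quantity that the display does not show.

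**3. Denominators.** Everyone starts on assigned drug, so the first two columns hold 3,500 each. Those who withdraw also enter the third. The column totals are then 7,000 + 525 = 7,525 to 7,000 + 700 = 7,700, against 7,000 randomized. Follow-up in the third column starts at withdrawal and is shorter. A proportion of subjects is not comparable across such columns, whereas a rate per person-year has a defined denominator in each.

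**4. Where a given LDM event lands.**

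| Event in an LDM participant | By assignment | By treatment at time of event |
|---|---|---|
| Toxicity that leads to the stop | LDM | LDM |
| Onset after withdrawal | LDM | Off, pooled |
| Onset during a temporary hold | LDM | Not stated |

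**5. Illustration; every event rate and late-onset share here is assumed.** Take 4% of 3,500 = 140 LDM participants with an event and 2% of 3,500 = 70 on placebo. By assignment the ratio is 140/70 = 2.00 whatever happens after stopping. Suppose 10%, 25% or 50% of the excess of 70 has its onset after the stop, and keep 3,500 as each denominator:

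| LDM events moved | Left in LDM column | No placebo events moved (70 left) | 5% moved (66.5 left) | 10% moved (63 left) |
|---|---|---|---|---|
| 7 | 133 | 1.90 | 2.00 | 2.11 |
| 17.5 | 122.5 | 1.75 | 1.84 | 1.94 |
| 35 | 105 | 1.50 | 1.58 | 1.67 |

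The on-treatment ratio falls below the by-assignment ratio only if LDM loses a larger share of its events than placebo. The documents do not give either share.

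**The case against.** The case against the point is substantial.

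- The sentence that introduces the three columns also commits to a summary by randomized assignment. A reader might infer from the three-column layout that LDM toxicity disappears from the report. It does not: every post-withdrawal LDM event stays with LDM in the by-assignment summary.
- Classification is by when the event occurred, not by when it was recorded. A reader might also infer that the toxicity prompting a stop leaves the LDM column, or that serious consequences commonly follow the stop. The first contradicts the text, and the second has no figure behind it in the documents.
- The signal linked to stopping appears elsewhere. SAP 4.4 tabulates by group the events that led to withdrawal or a dose change, and SAP 4.5 summarizes reasons for withdrawal by randomized arm.
- The formal comparison is arguably already by assignment. Net clinical benefit or harm is a secondary endpoint with a test of proportions (SAP 4.3), and the same section places pre-specified secondary analyses on randomized assignment.
- Treatment received in SAP 2.1 and 4.1 can be read at subject level: someone who took LDM and stopped has still received it. On that reading those sections do not point to the three-column display, and the proportion measure is not expressly attached to it.
- The arm split can partly be recovered by subtracting on-treatment counts from by-assignment counts.

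Most of this stands and sets the limits of the point. Three parts do not close it. Subtraction finds only participants whose events were all off treatment; it misses those with events in both states and supplies no person-time. The rule in SAP 4.3 sits beside a different general rule for safety in SAP 4.1, so the grouping for the adverse-event test is still open. If treatment received has a subject-level meaning, the SAP should say so, because the closing paragraph of 4.4 uses actual treatment in another sense.

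**Conclusion.** The point holds as a limited defect in one of two planned displays, together with an unstated order of precedence between them. In the display by treatment at time of event, the off-treatment column pools the arms, has no comparator, and has no stated lag window or person-time denominator. LDM events with onset after withdrawal leave the LDM column there. They remain in the by-assignment summary, so the documents do not support a claim that harm is concealed or lost.

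The size of any distortion cannot be determined from the documents. The only planning figure is about 350 LDM participants off drug but still followed. The ratios in the illustration rest on assumed rates and can move either way. This is a cheap improvement to the tables and does not threaten the trial's safety conclusions, provided the by-assignment summary is the one relied on.

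**What to change.** 1. Split the third column by randomized arm (Off LDM, Off placebo).
2. In the display by treatment at time of event, report events per 100 person-years, with the person-time shown for each column, and state how temporary holds are classified.
3. State in SAP 2.1, 4.1 and 4.4 that the by-assignment summary is the main between-arm safety comparison and that the other display is supportive. Say in SAP 4.3 that the net clinical benefit or harm table uses randomized assignment.
4. Optionally, add a fixed window after the last dose during which events stay with the treatment just stopped. Its length is a convention, so it should be set in advance.

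The cost is a few sentences of text and revised table shells. No new data are needed: classifying events by treatment at onset already requires the date of withdrawal, and that date also gives the person-time.

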4.5. Other Analysis

The following will be summarized by randomized treatment with frequency counts and percentages:

- Completion and withdrawal from the randomized treatment period
- Reason for withdrawal from the randomized treatment period
- Compliance
- Prior and concomitant medication
- Misrandomization

5.0. INTERIM ANALYSES

5.1. Interim Feasibility Analysis

An interim feasibility analysis will be performed jointly by the DSMB and the NHLBI after 1000 patients have been randomized and followed for at least 6 months. At this time, trial feasibility and safety will be reviewed, the trial dose range will be evaluated, suitability of the trial algorithms considered, and recommendations will be made to the investigators with regard to any needed protocol changes at that time.

Thus, for the purposes of the feasibility analysis, the investigators will submit a report to the NHLBI including the cumulative recruitment experience to date, the adherence among randomized participants, the rates of adverse events both overall and according to the major disease categories and the percent of participants willing to continue. It is expected that this report will pool information across treatment groups (i.e. maintain the treatment blind). However, a parallel report with information by treatment group will be submitted simultaneously to the trial's Independent Data and Safety Monitoring Board.

5.2. DSMB Analyses

Interim analyses of rates of the primary outcome, as well as rates of the individual components of the composite endpoint, and the pre-specified secondary endpoints will be prepared for presentation to the Data and Safety Monitoring Board (DSMB). Reports to the DSMB will also include comparisons of baseline characteristics between treatment groups, displays of cumulative recruitment by study time, comparisons of post-randomization laboratory values by treatment group, and rates of adverse events, both overall and within systems, by treatment group. The frequency of the meetings will be determined by the independent DSMB appointed by the NHLBI.

Specifically, the blinded portion of the report will display, by treatment group and visit number, the number of subjects with an expected visit (i.e. those whose window for that visit closed at least 4 weeks before database lock for the particular interim report), the number and percent of those who remained on drug at that visit, and secondary tables which display the numbers of subjects who gave scheduled blood samples. An additional table will display by treatment group the numbers of subjects who remain in study and on drug, and, for those who have discontinued, the reason for discontinuation. Categories for reasons for stopping which we have used in the past are: Adverse Event, Endpoint, Deceased, Medication Use, Investigator Decision, Site Closure, Protocol Noncompliance, Lost to Follow-up, Withdrew Consent, Other, and Unknown. Additional tables will display, by treatment group and visit number, the rates of adherence based on self-reported pill counts. These last tables will be shown two ways: first, restricted to subjects who attended a visit, and then with 0 imputed for adherence for subjects who missed a visit and whose visit window closed more than 12 weeks before database lock for that interim report. Overall, power for the trial was estimated under the assumption of a 5% annual drop-out and loss to follow-up rate. If the rate exceeds this amount at a scheduled interim report, study power will be re-estimated based on the observed rate.

While the frequency of meetings and the approach to interim monitoring will be the choice of the DSMB, we anticipate at least twice yearly meetings to monitor recruitment and retention, with quarterly safety reports. With respect to efficacy monitoring and possible stopping for benefit, we will recommend to the DSMB monitoring via the Lan-DeMets procedure¹⁹ with spending function $\alpha(t^*) = 2 - 2\Phi(Z_{\alpha/2}/\sqrt{t^*})$, where t^* is the information fraction, Φ is the standard normal distribution function, α is the two-sided type 1 error rate, and $Z_{\alpha/2}$ is its 100(1- $\alpha/2$)th percentile. To preserve alpha and to minimize the likelihood of an inflated effect estimate associated with early stopping, we recommend pre-specification of only two formal evaluations of efficacy. With an event-driven trial targeting 530 total confirmed endpoints, these evaluations would occur upon accrual of 199 and 398 confirmed primary endpoints. The Z-values for the boundaries would be ± 3.4786 at the first interim analysis and ± 2.3431 at the second efficacy analysis. Based on the formula of Schoenfeld²⁰, the Z-value is related to the expected value of the log-rank statistic by the formula $Z = \log(HR)\sqrt{D/4}$, where HR is the hazard ratio, and D is the overall number of events. Thus, with D=199 and 398, the hazard ratios at the boundary would be 0.611 and 0.791, respectively.

The DSMB has voted to prefer more conservative boundaries, and chose a P-value of 0.0001 at both information times, which corresponds to a Z-value of ± 3.891 . Approximate hazard ratios associated with this Z-value are 0.620 at 50% information and 0.677 at 75% information.

As a guideline for considering a recommendation to stop the study early because of convincing evidence of inefficacy (futility), pre-planned inefficacy bounds will also be considered upon accrual of 50% and again upon accrual of 75% of the targeted numbers of confirmed primary endpoints, i.e. upon accrual of 265 and 398 confirmed primary endpoints. These time

points agree with the cutpoints used in the AIM-HIGH trial²¹, and are chosen to mitigate the possibility of stopping early with an imprecisely estimated treatment effect. Based upon the Linear 20% Inefficacy Boundary approach described by Freidlin et al²², the inefficacy boundary will be crossed if the observed relative hazard of the primary endpoint associated with methotrexate assignment is greater than 0.99 at the first interim futility analysis, or is greater than 0.97 at the second interim futility analysis. Simulations performed by Freidlin et al indicate that their Linear 20% Inefficacy Boundary approach is associated with a less than 1% loss of power due to inefficacy monitoring. Further, their approach is more conservative than a 10 or 30% conditional power approach in later follow-up (i.e. after 70% of information is accrued). However, the Linear 20% Inefficacy Boundary approach is more aggressive than a 10% (or even a 20%) conditional power rule at the 50% information accrual point, so a more conservative boundary of an observed relative hazard associated with methotrexate assignment greater than 1.11 at the first interim futility analysis (the cutpoint associated with conditional power below 10%), may be preferred at that time, especially as use of this cutpoint will preserve power.

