5.5. Interim DSMB Analyses

Interim analyses of rates of the primary outcome, as well as rates of the individual components of the composite endpoint, and the pre-specified secondary endpoints will be prepared for presentation to the Data and Safety Monitoring Board (DSMB). Reports to the DSMB will also include comparisons of baseline characteristics between treatment groups, displays of cumulative recruitment by study time, comparisons of post-randomization laboratory values by treatment group, and rates of adverse events, both overall and within systems, by treatment group. The frequency of the meetings will be determined by the independent DSMB appointed by the NHLBI.

While the frequency of meetings and the approach to interim monitoring will be the choice of the DSMB, we anticipate at least twice yearly meetings to monitor recruitment and retention, with quarterly safety reports. To preserve alpha and to minimize the likelihood of an inflated effect estimate associated with early stopping, pre-planned efficacy analyses will occur only upon accrual of 50% and 75% of the planned study endpoints, i.e. 265 and 398 confirmed primary endpoints. Additional interim analyses of efficacy data may be carried out by the DSMB. The design of the trial, including evaluation of the implications of interim monitoring on study power, considered that stopping boundaries would be based on an alpha-spending function that approximates an O'Brien-Fleming boundary. Specifically, efficacy monitoring would utilize the Lan-DeMets procedure with spending function $\alpha(t^*) = 2 - 2\Phi(Z\alpha/2/\sqrt{t^*})$, where t^* is the information fraction, Φ is the standard normal distribution function, α is the two-sided type 1 error rate, and $Z\alpha/2$ is its 100(1- $\alpha/2$)th percentile. Under this approach, the Z-values for the boundaries at the 50% and 75% information times would be ± 2.963 and ± 2.359 , respectively, corresponding to two-sided P-values of 0.0030 and 0.0183, and observed hazard ratios of 0.695 and 0.789, respectively.

The DSMB has voted to prefer more conservative boundaries, and chose a P-value of 0.0001 at both information times, which corresponds to a Z-value of ± 3.891 . Approximate hazard ratios associated with this Z-value are 0.620 at 50% information and 0.677 at 75% information.

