As a consequence of these intended changes, the anticipated trial sample size was reduced from 7,000 to 5,500 and the targeted number of primary endpoints (now MACE-plus) was increased from 530 to 634 to have 90% power to detect a 23% reduction in the hazard of MACE-plus. However, while approved by the NHLBI External Advisory panel, the formal amendment to alter the protocol had yet to be submitted for IRB approval at the time of the first formal IDSMB meeting occurred to address efficacy and futility (upon accrual of half of the required MACE and MACE-plus endpoints) on March 13, 2018. At that meeting, the IDSMB recommended early termination of the trial based on crossing a pre-specified boundary for futility and absence of evidence for reduction in hsCRP with LD-MTX treatment. The IDSMB further asked for a formal safety follow-up visit for all participants after an additional 6 months of follow-up. These recommendations were accepted by the NHLBI in April 2018.

For the above reasons, the original Statistical Analysis Plan for the trial did not undergo formal revision (and is presented in full below). However, to be consistent with investigator intent and actions taken by the IDSMB, both the MACE and MACE-plus endpoints are presented in the primary report.

Statistical Analysis Plan

Cardiovascular Inflammation Reduction Trial (CIRT):

A randomized, double-blind, placebo-controlled, event-driven trial of weekly low-dose methotrexate (LDM) in the prevention of recurrent cardiovascular events among stable post-myocardial infarction patients with type 2 diabetes or metabolic syndrome

**Center for Cardiovascular Disease Prevention
Brigham and Women's Hospital**

Funding: National Heart Lung and Blood Institute

March 25, 2013

Abbreviations

ALT	Alanine aminotrasferase
AST	Aspartate aminotransferase
CIRT	Cardiovascular Inflammation Reduction Trial
CRP	C reactive protein
DSMB	Data Safety and Monitoring Board
HbA1c	Hemoglobin A1c
HDL-C	High density lipoprotein cholesterol
ITT	Intention to Treat
LDM	Low dose methotrexate
LDL-C	Low density lipoprotein cholesterol
MACE	Major Adverse Cardiovascular Event
NHLBI	National Heart Lung and Blood Institute
SAE	Serious adverse event
SD	Standard deviation
WBC	White blood cell count

Table of Contents

1.0. STUDY DETAILS	4
1.1. Study Objectives	4
1.2. Study Design	4
1.3. Number of Subjects	5
2.0. ANALYSIS SETS	6
2.1. Definition of Analysis Sets	6
2.2. Violations and Deviations	6

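### Does the 199/398-event schedule left in SAP 5.2 make the adopted efficacy stopping rule ambiguous?

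*Combined protocol and SAP*

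**What the plan says.** SAP 5.2 (DSMB Analyses) first leaves the approach to interim monitoring to the DSMB and then gives the investigators' advice: "we recommend pre-specification of only two formal evaluations of efficacy". With a target of 530 events, "these evaluations would occur upon accrual of 199 and 398 confirmed primary endpoints", at Z = ±3.4786 and ±2.3431. The section converts these with Schoenfeld's relation: "Thus, with D=199 and 398, the hazard ratios at the boundary would be 0.611 and 0.791, respectively". The spending function is written with an alpha that "is the two-sided type 1 error rate", and protocol 5.5 carries the same definition.

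The next paragraph of SAP 5.2 reports that the DSMB preferred stricter boundaries and "chose a P-value of 0.0001 at both information times", that is |Z| = 3.891. It continues: "Approximate hazard ratios associated with this Z-value are 0.620 at 50% information and 0.677 at 75% information". The futility paragraph that follows equates the same two fractions, 50% and 75%, with 265 and 398 events.

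Protocol 5.5 (Interim DSMB Analyses), in both protocol versions, states: "pre-planned efficacy analyses will occur only upon accrual of 50% and 75% of the planned study endpoints, i.e. 265 and 398 confirmed primary endpoints". For those times it prints Lan-DeMets boundaries of ±2.963 and ±2.359 (hazard ratios 0.695 and 0.789), and then reports the same DSMB vote.

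The SAP's introductory note dates the first formal efficacy and futility meeting by reference to events: "upon accrual of half of the required MACE and MACE-plus endpoints". SAP 4.3 and protocol 5.1 set the primary test at a two-sided 0.05 level. Neither document prints a critical value for the final look.

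**The concern.** Read in order, SAP 5.2 names only one pair of efficacy looks, 37.5% and 75%, before saying that the DSMB set one P-value at both times. A reader could carry the 199-event look forward into the adopted rule. The cutoff printed next to it, 0.620, does not belong to 199 events.

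The spending function adds to the doubt. Programmed with alpha as labelled, it gives boundaries looser than those printed. The two rules also need different final critical values, and none is printed. At stake would be an unclear stopping rule: an efficacy look at the wrong event count, a boundary that the stated formula does not reproduce, or a final test that fails to hold the 0.05 level.

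**Working it through.** **Inputs.** Target 530 events; recommended looks at 199 and 398 (SAP 5.2); pre-planned looks at 265 and 398 (protocol 5.5); adopted |Z| = 3.891 (both documents); 1:1 allocation (SAP 1.2); two-sided level 0.05 (SAP 4.3, protocol 5.1).

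**1. Information fractions.** 199/530 = 37.5%; 265/530 = 50%; 398/530 = 75%.

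**2. Hazard ratios.** The SAP's relation Z = log(HR)·√(D/4) gives, on the benefit side, HR = exp(−2|Z|/√D).

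| Rule | Z | Events | HR computed | HR printed |
|---|---|---|---|---|
| SAP recommendation | 3.4786 | 199 | 0.611 | 0.611 |
| SAP recommendation | 2.3431 | 398 | 0.791 | 0.791 |
| Protocol Lan-DeMets | 2.963 | 265 | 0.695 | 0.695 |
| Protocol Lan-DeMets | 2.359 | 398 | 0.789 | 0.789 |
| Adopted by DSMB | 3.891 | 265 | 0.620 | 0.620 (50%) |
| Adopted by DSMB | 3.891 | 398 | 0.677 | 0.677 (75%) |
| Adopted Z at the recommended first look | 3.891 | 199 | 0.576 | not printed |

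Every printed hazard ratio is right for the count or fraction attached to it. As a check, 4 × 3.891²/(ln 0.620)² = 265.0 events. The SAP nowhere attaches 0.620 to 199 events.

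**3. Spending function.** At the first look, the boundary's two-sided P must equal the alpha spent.

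- As labelled (alpha = 0.05), at 50%: 2 − 2Φ(1.96/√0.5) = 0.00557. The printed P is 0.0030.
- With 0.025 in each tail, at 50%: 4 − 4Φ(2.2414/√0.5) = 0.00305, which gives Z = 2.963 as printed.
- With 0.025 in each tail, at 37.5%: 4 − 4Φ(2.2414/√0.375) = 0.00050, which gives Z = 3.4786 as printed.

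Recursive numerical integration gives the second looks. With 0.025 per tail the pairs are 2.963/2.359 and 3.4786/2.3431, all as printed. With the literal label they are 2.772/2.298 and 3.201/2.272, which appear in neither document. The printed Z-values are therefore correct for an overall two-sided 0.05; only the label is wrong.

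**4. Overall alpha under the adopted rule.** A simple upper bound adds the three tests: 0.0001 + 0.0001 + 0.05 = 0.0502. Integration that allows for the correlation between looks, with a final 1.96, gives:

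- looks at 50% and 75%: 0.05001
- looks at 37.5% and 75%: 0.05002
- looks at 37.5%, 50% and 75%: 0.05003

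The final critical value that makes alpha exactly 0.05 with looks at 50% and 75% is 1.9600 (P = 0.04999).

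**The case for a change.** The strongest case for a change is that the SAP is the published analysis plan, presented in full and never formally revised, and should be readable without the protocol. It records a change of boundary but not the accompanying move of the first look from 37.5% to 50%. It defines alpha in a way that does not reproduce its own numbers. It also sets two rules side by side that end at different critical values: 1.96 for the adopted rule, and 2.014 for Lan-DeMets with looks at 50% and 75%. Pairing the printed 50%/75% Lan-DeMets boundaries with a final 1.96 would give an overall alpha of 0.0554.

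Part of this stands. One clause is missing on the timing of the first look, and the alpha label is a slip in both documents.

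The rest does not lead to a change. The sentence right after the DSMB's choice names 50% and 75%, the total of 530 is given in the paragraph before, and the paragraph after prints the conversion to 265 and 398 events. An analyst can obtain the count from SAP 5.2 alone, without back-solving a hazard ratio, and protocol 5.5 confirms it for efficacy. The 0.0554 figure needs a pairing that neither document proposes: anyone using the spending function would take its own final boundary, and under the adopted rule the stated 0.05 level gives 1.96.

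**Conclusion.** No change to the plan is needed. The 199/398 block is a recommendation left on the page after the DSMB chose otherwise. The alpha label is a clerical slip in a rule that was not adopted, whose printed boundaries are correct. The final critical value is a detail that follows from the stated test level. Rewording would alter no boundary in force, no error rate and no conclusion: the adopted rule is |Z| ≥ 3.891 at 265 events (HR 0.620) and at 398 events (HR 0.677), with overall alpha 0.0500 to four decimals. Even a literal misreading that put the first look at 199 events would leave alpha at 0.05002.

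Conduct agreed with the 50% reading, since the first formal review came at half of the required endpoints. The SAP's introductory note gives crossing of a futility boundary and absence of hsCRP reduction as the grounds for stopping, so the efficacy boundary was not what ended the trial.

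The alpha figures assume a final test at 1.96, inferred from the two-sided 0.05 level, and interim efficacy tests only at the times shown in the working, all at 3.891. Protocol 5.5 lets the DSMB add efficacy analyses without stating their number or threshold, and the figures do not cover looks beyond those computed.
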